7.5 SECONDARY OBJECTIVE ANALYSIS

[figure not shown]
This section is not applicable as no secondary endpoint has been specified in the protocol.

[figure not shown]
**Boehringer Ingelheim
TRIAL STATISTICAL ANALYSIS PLAN
1199-0434**

Page 20 of 33

c40328414-01

Proprietary confidential information © 2025 Boehringer Ingelheim International GmbH or one or more of its affiliated companies.

7.7 EXTENT OF EXPOSURE

Exposure summary will be presented over 52 weeks. The duration on treatment and dose intensity will be computed overall, as well as on the individual dose strengths.

In case last drug administration date is incomplete, assume all prescribed medication at the last clinical visit have been taken. Impute the last drug administration date based on the last clinical visit date and number of capsules dispensed, it could be the end of study date if the imputed last drug administration date occurs after the end of study date.

A summary of treatment interruptions will be created including number of patients with at least one interruption, number and reason of interruptions. A similar summary will be performed for dose changes. Reasons for dose reduction or interruption will be presented.

Duration of exposure [months] = (date of last drug administration – date of first drug administration +1 day) / 30.5

Duration of exposure in categories: ≤3 months (91 days); >3 months (91 days) to ≤ 6 months (182 days); > 6 months (182 days) to ≤12 months (365 days)

Treatment interruptions will not be subtracted from the duration of exposure.

Duration on actual dose (100 or 150 mg bid) (sum of durations on-treatment for each dose effectively taken): in weeks and in categories (≤ 8 weeks, > 8 weeks)

Total dose [g]: Duration of exposure [days] * actual dose [g]

Dose intensity [%]: amount of drug actually administered over the study (dose 100mg and 150mg) divided by the amount of drug that would have been administered had dose 150mg bid been administered over all the study (from date of first administration to date of last administration, whether or not trial drug was prematurely discontinued). Dose intensity will be summarized in percent and in categories (≤ 30 %, >30% - ≤50%, >50% - ≤90%, >90% - <100%, 100%).

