4.1.4 Drug assignment and administration of doses for each patient

Table 4.1.4: 1 Dosage and treatment schedule

Treatment arm	Nintedanib 150 mg	Placebo matching 150 mg	Nintedanib 150 mg	Placebo matching 150 mg
	Morning		Evening	
Nintedanib 150 mg	1		1	
Placebo		1		1

Based on the treatment allocated at randomization, the IRT system will be used to dispense the appropriate medication kits at each visit. Patient will receive either active drug at a dosage of 150 mg bid or placebo bid.

The patients should take the trial medication with food, swallow whole with water, and should not be chewed or crushed because of a bitter taste, and should observe a dose interval of 12 hours as far as possible. Effort should be made to ensure that drug administration occurs at the same time every day +/- 30 min (between 06:00 and 11:00 in the morning, and between 18:00 and 23:00 in the evening). A forgotten dose should be skipped if the time window to the next dose is less than 8 hours. The next dose should be taken as scheduled. The recommended maximum daily dose of 300 mg should not be exceeded.

The dose may be reduced to 100 mg bid due to AE after the investigator assessment. The investigator can dispense new medication kits with 100mg to the patient via IRT system.

A patient diary will be used to record the daily intake of the trial medication.

Trial medication will consist of 1 capsule twice daily (bid) administered orally throughout the study. Wallets covering 30 days + 5 days reserve treatment will be dispensed to the patient:

- 1 wallet at Day 1 (randomization = Visit 2) (30 days plus 5 days reserve)
- 2 wallets from Visit 4 (60 days plus 10 days reserve)
- 3 wallets from Visit 6 (90 days plus 15 days reserve)
- 3 Wallets from Visit 7 (90 days plus 15 days reserve)
- 4 wallets from Visit 8 (120 days plus 20 days reserve)

To ensure patients receive adequate supply of study medication, kits will be dispensed at clinical visits in quantities as outlined in [Table 4.1.4: 2](#).

Table 4.1.4: 2 Number of IMP kits dispensed at each visit

Study visits	2	3	4	5	6	6a	7	7a	8	8a	9
Number of											
IMP kits dispensed	1	—	2	—	3	—	3	—	4	—	—

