6.2.3 Follow-up period and trial completion

A Follow-up Visit has to be scheduled 7 days after End of Treatment Visit for all patients. This Follow-up Visit is the safety follow-up after treatment discontinuation.

- Physical examination including vital signs.
- Adverse events and concomitant therapy will be assessment since last visit.
- Local dipstick pregnancy test (if applicable).
- Spirometry (FVC) in the allowed time window will be performed.

Patient's participation will be concluded for all subjects who complete all treatment visits.

Trial completion

The trial completion eCRF page has to be filled-in when the patient has terminated the trial. The end of the trial for the individual patient is:

Proprietary confidential information © 2025 Boehringer Ingelheim International GmbH or one or more of its affiliated companies

- For patients who complete all study visits, end of trial is follow-up (FU) visit (after the end of treatment visit (EOT)).
- For patients who discontinue trial medication prematurely during the study period and complete an End of Treatment (EOT) visit and a Follow-up (FU) visit 1 week later, end of trial is visit at Week 52.
- For patients who withdraw consent, end of trial is the date of consent withdrawn

Patients who prematurely discontinued trial medication

In case a patient has to permanently discontinue trial medication, for whatever reason, he/she will be encouraged to attend all future visits up to end of trial as originally planned (except for the laboratory 'a-Visits').

1. During these visits, the patient will undergo all planned examinations according to [Flow Chart](#), especially spirometry (FVC) and [REDACTED] however he/she will not have to [REDACTED] safety laboratory.
2. These visits will be regarded as part of the trial despite the patient having discontinued trial medication.

The need for coming to future visits in case of prematurely discontinuation of trial medication will be explained to patients prior to their participation in the trial.

Vital status information

In case of premature discontinuation of trial medication, if the patient does not attend future visits as planned, every attempt will be made to get information on vital status at 52 weeks after his/her randomization and at the end of the trial for patients who have withdrawn consent.

Patients will be asked to agree to be contacted by the site personnel, which could be by telephone calls, to allow collection of the vital status.

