7.4.3 Supplementary analysis

A supplementary analysis including only on-treatment measurements of FVC (ml) will be analyzed. This analysis reflects the expected biologic effect of nintedanib 150 mg bid in the treatment of patients with PF-ILD.

FVC collected from the first drug administration up to the last drug intake plus one day will be included in analysis. The same RSI model used in the main analysis will be applied (see [Section 7.4.1](#)). Point estimate and two-sided 95% CI of the treatment effect will be presented. Tables presenting the results of the supplementary analysis will be created in addition to graphical representations.

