7.8.1 Adverse events

Unless otherwise specified, the analyses of AEs will be descriptive in nature. All analyses of AEs will be based on the number of subjects with AEs and NOT on the number of AEs. For further details on handling of missing or incomplete AE dates and summarization of AE data, please refer to ([9.2](#), [9.4](#)).

The analysis of AEs will be based on the concept of treatment emergent adverse events (TEAEs). That means that all AEs occurring between first drug intake till 7 days after last drug intake will be assigned to the randomized treatment. All AEs occurring before first drug intake will be assigned to ‘screening’ and all AEs occurring after last drug intake + 7 days will be assigned to ‘follow-up’ (for listings only). For details on the treatment definition, see [Section 6.1](#).

According to ICH E3 ([9.7](#)), in addition to deaths and serious adverse events, ‘other significant’ AEs need to be listed in the clinical trial report. These will be any non-serious adverse event that led to an action taken with study drug (e.g., discontinuation or dose reduced). An overall summary of adverse events will be presented.

The frequency of subjects with AEs will be summarized by treatment, primary system organ class and PT (mention MedDRA levels to be displayed in the tables). Separate tables will be provided for subjects with SAEs, other significant AEs, AEs leading to permanent dose reduction, AEs leading to treatment discontinuation, AEs of at least moderate severity, drug-

related AEs, drug-related SAEs, adverse events leading to death and adverse events of special interest (AESI). In addition, selected safety topics / user-defined AE categories (UDAECs) will be summarized by treatment group, these selected AE topics will be determined by medical review and documented prior to DBL.

The system organ classes will be sorted by default alphabetically, PTs will be sorted by frequency (within SOC).

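### SAP 7.7 dates an incomplete last dose as if every dispensed capsule, reserve included, had been taken, which can place it 7 to 21 days past the next dispensing visit

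*SAP*

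**What the plan says.** SAP 7.7 holds the only visible rule for an incomplete last-dose date: "In case last drug administration date is incomplete, assume all prescribed medication at the last clinical visit have been taken". The analyst is then to "Impute the last drug administration date based on the last clinical visit date and number of capsules dispensed". One limit follows: "it could be the end of study date if the imputed last drug administration date occurs after the end of study date". The rule does not mention the known part of a partial date, reserve capsules, returned capsules, the intake diary, the EOT visit or death.

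Protocol 4.1.4 sets the supply: "Wallets covering 30 days + 5 days reserve treatment will be dispensed to the patient". One wallet is given at Visit 2, two at Visit 4, three each at Visits 6 and 7, and four at Visit 8. The Flow Chart has trial drug collected at Visits 4, 6, 7, 8 and 9 and at EOT.

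Protocol 6.2.3 defines the end of trial for each patient. For those who stop drug early but stay in the trial, "end of trial is visit at Week 52". For completers it is the follow-up visit, and after withdrawal of consent it is the withdrawal date.

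Three other sections depend on the last-dose date. SAP 7.4.3: "FVC collected from the first drug administration up to the last drug intake plus one day will be included in analysis". SAP 7.8.1 assigns to treatment "all AEs occurring between first drug intake till 7 days after last drug intake". SAP 7.3 builds the compliance denominator from the first and last intake dates. None of them refers to 7.7.

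**The concern.** The rule treats reserve capsules as swallowed, although the reserve is there to cover late visits and leftovers are handed back at the next collection visit. A date derived this way can fall after the capsules it relies on have left the patient's hands. Because the rule ignores the known part of a partial date, it can also contradict a recorded month or year.

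The starting point is unclear as well. Patients who stop drug early are asked to keep attending, so their last clinical visit may be one at which nothing was dispensed.

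Exposure in 7.7 is overstated directly. If the same date is carried into 7.3, 7.4.3 or 7.8.1, measurements and events after the real stop are labelled on-treatment, and compliance is divided by days on which no drug was taken. The supplementary FVC analysis is meant to describe the drug's biological effect, so off-drug measurements are unwelcome there, with only about 30 placebo patients.

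**Working it through.** **Inputs.** Wallet content and number: Protocol 4.1.4. Visit days from the Flow Chart: Visit 2 = 1, Visit 4 = 29, Visit 6 = 85, Visit 7 = 169, Visit 8 = 253, Visit 9 = 365. Visit windows: ±3 days to Visit 6, ±7 days for Visits 6a to 9; follow-up is 7 days after EOT, with a +3 window. I take the SAP's end-of-study date to be the individual end of trial in Protocol 6.2.3, and the last clinical visit to be the last visit at which drug was dispensed.

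**Check of the plan's own figures.** Wallets × 35 gives 35, 70, 105, 105 and 140 days. Protocol 4.1.4 states 30+5, 60+10, 90+15, 90+15 and 120+20, so they agree.

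**Supply against the interval.** Excess = supply − gap. Imputed day = dispensing day + supply − 1.

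| Dispensed at | Supply (days) | Gap to next collection visit | Excess | Imputed day, no cap |
|---|---|---|---|---|
| Visit 2 | 35 | 29 − 1 = 28 | 7 | 35 |
| Visit 4 | 70 | 85 − 29 = 56 | 14 | 98 |
| Visit 6 | 105 | 169 − 85 = 84 | 21 | 189 |
| Visit 7 | 105 | 253 − 169 = 84 | 21 | 273 |
| Visit 8 | 140 | 365 − 253 = 112 | 28 | 392 |

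Counting the dispensing day as the first dosing day makes the overshoot one day shorter (6, 13, 20, 20, 27). Visit windows spread the first four excesses to 4–10, 8–20, 11–31 and 7–35 days. Without the reserve they would be 2, 4, 6 and 6 days, and 8 for Visit 8.

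**Applying the cap.** The imputed days for Visits 2, 4, 6 and 7 supply (35, 98, 189, 273) all precede day 365, so the cap does nothing for a patient followed to Week 52. For Visit 8 supply it binds:

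- Completer: min(392, 372) = 372, which is 372 − 365 = 7 days past Visit 9 (375, or 10 days, with the +3 window).
- Premature discontinuer: min(392, 365) = 365, which is 0 days past Visit 9.

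**Largest error.** If the drug was stopped soon after dispensing, the error is close to the whole supply: about 105 days for Visits 6 and 7. For Visit 8 in a premature discontinuer the cap makes it 365 − 253 = 112 days.

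**Example, if the date is reused.** A patient is supplied at Visit 6, takes the last dose on day 90, keeps attending, and has an incomplete date.

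- Imputed day 189, an error of 189 − 90 = 99 days, more than three months even if the true month was recorded.
- SAP 7.4.3 window: to day 190 instead of 91. The Visit 7 FVC on day 169, 79 days after the last dose, counts as on-treatment.
- SAP 7.8.1 window: to day 196 instead of 97.
- SAP 7.3, with full adherence and a complete capsule count: 180 capsules taken. True denominator 90 × 2 = 180, giving 100%. Imputed denominator 189 × 2 = 378, giving 180/378 = 47.6%, the lowest category.

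**The case against.** The strongest reply is that the rule is confined. It stands under extent of exposure, and 7.4.3, 7.8.1 and 7.3 do not cite it. A reader might infer that on-treatment FVC and adverse events are certainly misplaced; the documents neither state nor exclude that reuse, so the effect is conditional. This stands.

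A reader might also multiply out the Visit 8 supply and infer a date 28 days past Visit 9, or a 140-day error for an early stop. The end-of-study limit in the same SAP sentence rules out both at nominal timing. Nor is it right that the limit never acts for early stoppers: for Visit 8 supply it removes the whole overshoot.

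If the last clinical visit is literally the last one attended, there is no later visit to overshoot and no later scheduled on-site FVC to mislabel. That is fair for patients who leave. It does not help those who keep attending, for whom the literal reading may point to a visit with nothing dispensed and so give no usable date.

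Consequences are also limited. A wider treatment-emergent window usually errs on the cautious side for safety. For a completer who stopped at Visit 9, last dose plus 7 days already reaches day 372. SAP 7.3 does not calculate compliance when a capsule count is missing. The diary, the EOT visit and the IRT notification should keep incomplete dates rare.

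Finally, dating the last dose from capsules used at two per day, or from the last diary entry, can err the other way. Protocol 4.2.1 permits interruptions of up to 4 or 8 weeks, and a diary may be abandoned early. This stands and shapes the fix.

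**Conclusion.** The rule needs correcting, but the point is minor. At nominal timing the imputed date can fall 7, 14 or 21 days past the next dispensing visit, and past Visit 9 by about 7 days (at most 10) for completers and 0 for premature discontinuers. For someone who stopped soon after dispensing, the error can reach about 105 to 112 days. The rule can also contradict a known month or year.

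These figures rest on the reserve being counted, on the last clinical visit meaning the last dispensing visit, and on the SAP's end-of-study date being the protocol's individual end of trial. The effect on exposure is direct; the effect on 7.3, 7.4.3 and 7.8.1 depends on reuse of the date.

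A reader might infer that the main FVC estimate is at risk. It is not: under the treatment-policy strategy in SAP 6.3, data after discontinuation are kept, so the last-dose date does not select them. I have not calculated any bias in the supplementary estimate, because the documents do not give the number of incomplete dates. That it is small is an assumption.

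**What to change.** In SAP 7.7, define the starting point as the last visit at which drug was dispensed. Cap the imputed date at the earliest of:

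- the last day compatible with the recorded month and year;
- the next visit at which drug was collected, or EOT;
- death;
- end of study.

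Use the diary and the returned-capsule count, allowing for recorded interruptions, as supporting information only. State that the same last-dose date feeds 7.3, 7.4.3 and 7.8.1.

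The cost is a few lines of SAP text and a little programming with data already collected. The small downside is a slightly shorter exposure and treatment-emergent window for the patients affected.

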4.2 OTHER TREATMENTS, EMERGENCY PROCEDURES, RESTRICTIONS

4.2.1 Other treatments and emergency procedures

Rescue medication to reverse the action of nintedanib is not available.

Dose reduction from 150 mg bid to 100 mg bid or treatment interruption should be considered to manage adverse events. No further dose reduction is possible for patients on the 100 mg bid regimen. In case of persistent adverse events observed at this dose, or severe effects at 150 mg bid, permanent treatment discontinuation should be considered.

Treatment interruption, reduction and re-increase are allowed at multiple occasions.

Table 4.2.1: 1 Allowed treatment reduction / interruption periods:

	AEs considered related to study drug	AEs not considered related to study drug
Maximum interruption	4 weeks	8 weeks
Recommended restart	with reduced dose (100 mg bid)	with the same dose as before interruption (100 mg bid or 150 mg bid)
Re-escalation	within 4 weeks to 150 mg bid	N/A

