4.2.1.3 Management of acute ILD exacerbations

In case of acute ILD exacerbation (see [Section 5.1.2](#)), all treatment options considered adequate by the Investigator are allowed. The patient may interrupt study treatment for up to 8 weeks, if necessary (e.g. if short-term full anticoagulation is performed).

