6. GENERAL ANALYSIS DEFINITIONS

6.1 TREATMENT(S)

For the definition of treatment administered during the trial, see Section 4 of CTP.

- Screening: From informed consent to randomization
- Treatment period: From first trial drug intake to last trial drug intake
- Residual effect period / Safety follow-up: From the last trial drug intake plus 1 day to last trial drug intake plus 7 days
- Off-treatment period: From start date of trial drug interruption to re-start of trial drug

All analyses will be based on the planned treatment groups (Nintedanib 150 mg bid vs. Placebo) as randomized by IRT. The subjects will be analyzed according to the stratum to which they actually belong to, regardless of any stratification error at randomization.

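### SAP 7.7 total dose, read literally, counts interruption days as dosed; SAP 7.8.1 omits the protocol's rule on pre-treatment AEs that worsen (descriptive tables only)

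*SAP*

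**What the plan says.** **Exposure.** SAP 7.7 takes duration of exposure as last minus first administration date plus one day (divided by 30.5 for months) and adds: "Treatment interruptions will not be subtracted from the duration of exposure". Total dose follows as "Total dose [g]: Duration of exposure [days] * actual dose [g"]. Two other quantities in the section treat days off drug differently. Duration on actual dose, at 100 or 150 mg bid, is the "sum of durations on-treatment for each dose effectively taken". Dose intensity has as its numerator the "amount of drug actually administered over the study (dose 100mg and 150mg"), set against what 150 mg bid would have supplied between first and last administration. SAP 6.1 gives interruption days their own name: "Off-treatment period: From start date of trial drug interruption to re-start of trial drug". SAP 7.3 subtracts AE-related interruptions when it computes compliance.

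Interruptions are an expected part of conduct. Protocol 4.2.1 states: "Treatment interruption, reduction and re-increase are allowed at multiple occasions". Its Table 4.2.1:1 sets the maximum at 4 weeks for drug-related AEs and 8 weeks for unrelated ones. Protocol 4.2.1.3, on acute ILD exacerbations, says: "The patient may interrupt study treatment for up to 8 weeks".

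**Adverse events.** Protocol 7.2.5 counts as treatment-emergent the AEs that occur from start of treatment to 7 days after the last dose. It also counts AEs that begin before the first dose and worsen on treatment. SAP 7.8.1 uses the same window, but continues: "All AEs occurring before first drug intake will be assigned to" screening, with no exception for worsening.

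**The concern.** Total dose should report the grams of drug a patient received. If the multiplier includes days on which none was taken, the figure is closer to the drug that would have been given without a break. For a patient kept on 150 mg bid it then equals the denominator of dose intensity, not its numerator. Two lines of one exposure summary would rest on different amounts of drug, and a reader could not reconcile them.

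For AEs, the SAP says in section 3 that it is based on section 7 of the protocol, yet its rule is narrower than protocol 7.2.5. The treatment-emergent tables could depart from the protocol definition without a recorded reason.

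**Working it through.** **Total dose.** The plan states no figure here to reproduce, so I applied its formula to an illustrative patient.

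Inputs:
- Span D = 365 days (Day 1 to Day 365 in the protocol flow chart).
- Daily dose 0.3 g at 150 mg bid and 0.2 g at 100 mg bid (300 mg and 200 mg daily in the protocol synopsis).
- Days off I = 28 or 56, the 4- and 8-week maxima in protocol Table 4.2.1:1.
- Assumptions: every capsule is taken on non-interrupted days, and actual dose is one of the two strengths that the SAP names.

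Formulas at 150 mg bid: as written, D × 0.3; taken, (D − I) × 0.3; excess relative to drug taken, I / (D − I); dose intensity, (D − I) / D.

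| Days off | As written (g) | Taken (g) | Excess | Dose intensity |
|---|---|---|---|---|
| 0 | 365 × 0.3 = 109.5 | 109.5 | 0 | 100% |
| 28 | 109.5 | 337 × 0.3 = 101.1 | 8.4 g, 28/337 = 8.3% | 337/365 = 92.3% |
| 56 | 109.5 | 309 × 0.3 = 92.7 | 16.8 g, 56/309 = 18.1% | 309/365 = 84.7% |

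A patient with 28 days off and then 28 days at 100 mg bid takes 309 × 0.3 + 28 × 0.2 = 98.3 g. The formula does not say how to combine strengths. If they are summed, the result depends on which dose is carried through the days off:
- 150 mg bid: 337 × 0.3 + 28 × 0.2 = 106.7 g (+8.5%).
- 100 mg bid: 309 × 0.3 + 56 × 0.2 = 103.9 g (+5.7%).

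With the 28 reduced-dose days and no interruption, summing by strength gives 337 × 0.3 + 28 × 0.2 = 106.7 g both ways. The excess therefore comes from the days off, not from the reduction.

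**Treatment-emergent AEs.** No arithmetic applies. The two rules sort three kinds of AE as follows.

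| AE | Protocol 7.2.5 | SAP 7.8.1 |
|---|---|---|
| Begins before first dose, does not worsen | Not treatment-emergent | Screening |
| Begins before first dose, worsens on treatment, kept as one record | Treatment-emergent | Screening |
| Worsening entered as a new AE with on-treatment onset | Treatment-emergent | Treatment-emergent |

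The rules part only in the middle row. That row can occur: AEs are collected from consent (protocol 5.2.6.2.1) and screening may last 8 weeks (flow chart footnote). The readable text of SAP section 4 deals with the FVC data cut and the HRCT stratum and lists no change to the AE rule. The documents give no count of such AEs.

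**The case against.** The SAP never defines actual dose. If it is applied day by day and is zero while drug is stopped, there is no overcount. A programmer working by strength might also reach for duration on actual dose, which is on-treatment only. SAP 6.1 does not settle the matter, because it also defines a treatment period from first to last intake that spans interruptions. This stands, and it limits the point to what the formula gives when read literally. A reader might infer that total dose will be too high for every interrupted patient; the documents do not support that, because it depends on an undefined term.

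A reader might also infer that exposure will be overstated mainly in the nintedanib group, since interruption is a listed response to diarrhoea and raised liver enzymes. The documents give no interruption frequency overall or by arm, so neither a group mean nor a difference between arms can be derived. The 28- and 56-day cases are protocol maxima for one interruption, not typical values. SAP 7.7 also plans a separate summary of interruptions and their reasons, so they will be visible.

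On AEs, SAP 7.8.1 refers to a company standard on AE analysis (reference 9.4) that is not in the documents. It may contain the worsening rule; this cannot be confirmed either way. A reader might infer that the sponsor has dropped the protocol rule. Silence does not show that, particularly in a SAP that assumes familiarity with the protocol. Protocol 3.1 also gives the window without the worsening clause. What remains is that the SAP sentence makes no exception where protocol 7.2.5 does. Protocol 5.2.6.1.1 asks for worsening of pre-existing conditions to be recorded as an AE, which is the third row of the table and limits the effect.

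**Conclusion.** Both points hold in limited form, at low severity. Unless actual dose is zero on interruption days, SAP 7.7 counts those days as dosed, and its total dose cannot be reconciled with dose intensity. The size is +8.3% for 28 days off and +18.1% for 56 for the illustrative patient only, under the stated assumptions of one strength and full adherence. Keeping interruptions in duration of exposure is a valid convention and is not at issue.

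SAP 7.8.1 and protocol 7.2.5 differ on pre-treatment AEs that worsen, with no recorded reason in the readable text. The number affected is unknown and may be small.

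Only descriptive exposure and AE tables are touched. The FVC analysis does not use either quantity, and dose intensity as defined is not distorted.

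**What to change.** **SAP 7.7, one sentence.** Either of two routes works:
- Compute total dose from the same amount of drug actually administered that forms the dose-intensity numerator. The two lines then agree by construction.
- Sum, over strengths, the SAP's own duration on actual dose times the daily dose, excluding interruption days. Label this a nominal dose, because it ignores skipped capsules and may still differ from the dose-intensity numerator. For example, with 28 days off and an assumed 95% capsule intake on the other 337 days, it gives 101.1 g against 101.1 × 0.95 = 96.0 g taken.

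Leave duration of exposure as defined. No new data are needed. Compared with the literal formula, total dose falls for interrupted patients.

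**SAP 7.8.1, one sentence.** Add the protocol 7.2.5 clause on worsening, or record the departure and its reason in SAP section 4. If reference 9.4 already contains the rule, say so in the added sentence. Adding the clause depends on worsening being identifiable in the AE data, which the documents do not settle; if it is not, recording the departure is enough. Compared with the SAP rule as written, the treatment-emergent count can only stay the same or rise.
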